3.2 Number of Subjects

Our goal is to enroll 20 CPI-eligible patients onto the intermittent arm. We will first screen up to 50 patients for this study in order to get our target sample size. If, there are not at least 20 patients with a tumor burden reduction of 10% or greater, we will continue to screen up to 25 more patients (total of 75 patients). If we screen 75 patients without enrolling 20 patients into the intermittent arm, we will stop the trial and deem it not feasible (refer to section 14.1 for sample size justification)

3.3 Expected Duration of Treatment and Subject Participation

Each study cycle consists of 14-28 days, depending on which CPI is chosen. CPI of choice will be administered on day 1.

All patients who do not meet criteria for the CPI intermittent phase of the study will be treated until unacceptable toxicity or RECIST-defined PD. Patients with RECIST-defined PD may continue CPI therapy at the discretion of the treating MD. These patients will continue with normal imaging every 12 weeks. In cases where a patient is continued on therapy after PD and develops subsequent PD ($\geq 20\%$ increase in sum of target lesions compared to the initial PD tumor measurements, the patient will come off study).

Patients who meet criteria for the intermittent phase (i.e., have $\geq 10\%$ tumor burden reduction) will not receive CPI therapy. Imaging will continue per protocol (every 12 weeks from the initial date they stopped CPI therapy). Patients who have RECIST defined PD on the intermittent phase should reinitiate CPI therapy. Patients who have a subsequent decrease in tumor burden $\geq 10\%$ can then restart CPI therapy as per protocol. (refer to schema in Section 3.1).

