Sample Size	20 patients that have enrolled into the intermittent arm
Disease sites/Conditions	Advanced urothelial carcinoma
Interventions	A phase II study conducted investigating the use of intermittent CPI therapy in cisplatin ineligible or treatment refractory patients with aUC who respond to therapy. Patients will be treated with CPI therapy for at least 20 weeks as per standard of care (SOC), at which time those with a tumor burden reduction of 10% or greater will suspend CPI therapy. Patients with a documented increase in ≥ 20% tumor burden (RECIST 1.1 PD) will re-initiate CPI. For those patients who continue to have response, they will remain off therapy.

ABBREVIATIONS

CCCC	Case Comprehensive Cancer Center
CRF	Case Report Form
DSTC	Data Safety and Toxicity Committee
FDA	Food and Drug Administration
ICF	Informed Consent Form
IRB	Institutional Review Board
PRMC	Protocol Review and Monitoring Committee
SOC	Standard of Care
CCF	Cleveland Clinic Foundation
UH	University Hospitals
aUC	Advanced urothelial carcinoma
CPI	Checkpoint inhibitor
OS	Overall survival
PFS	Progression free survival
TFI	Treatment Free Interval
ORR	Overall response rate

TABLE OF CONTENTS

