3.0 STUDY DESIGN

3.1 Study design including dose escalation / cohorts

¹Patients may be treated with any FDA-approved CPI for cisplatin-ineligible aUC or cisplatin resistant/refractory aUC.

²In cases where a patient is continued on therapy after PD and develops subsequent disease progression, CPI should be discontinued.

³Patients who do not have tumor burden reduction of >10% after 2 consecutive imaging will be removed from study.

* Of note all imaging is compared to scans done prior to intermittent therapy initiation.

A phase II study design to investigate the use of any CPI on an intermittent dosing schedule. Patients with aUC who treatment refractory or cisplatin ineligible will receive CPI of choice as per standard dosing. Patients who have initial $\geq 10\%$ tumor burden

reduction will discontinue the CPI until they experience a $\geq 20\%$ disease progression, at which time CPI therapy will be restarted.

The 10% cut off was chosen on the basis of a metanalysis in CPI-treated metastatic melanoma that this cut point may optimally separate overall survival in patients (better than the traditional RECIST PR 30% cut off) and also from prior experience using this cut off in an intermittent nivolumab trial in kidney cancer.^{28,42} Please refer to section 14.0 for statistical consideration, including early stopping rules.

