6.4 Criteria for Removal from Study

Patients will be treated per protocol until:

1. RECIST-PD (treating MD may continue CPI). Study PI must be informed via email (or Site Communication Form") that subject is continuing based on clinical benefit. These patients will continue per normal imaging schedule (every 12 weeks).
2. Patients on CPI treatment who develop a RECIST-PD (PD1) can continue CPI treatment if there is clinical benefit. If on subsequent imaging they continue to have RECIST-PD (PD2), they will be removed from trial.
3. Unacceptable toxicity (see Section 7.3)
4. Withdrawal of consent
5. General or specific changes in the patients' condition that render the patient unacceptable for further treatment in the judgment of the investigator.
6. Any patient who on consecutive imaging (i.e., for 24 weeks) has SD while on therapy and does not achieve > 10% tumor burden reduction will be removed from the trial.

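### Sections 3.3 and 6.4 give different triggers for leaving the trial at second progression on continued CPI, and no passage reconciles them

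*Combined protocol and SAP*

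**What the plan says.** Three places in the protocol deal with a patient who progresses on CPI, is kept on it, and then has a further scan.

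- **Section 3.3**, in the paragraph on patients who have not qualified for the intermittent phase: "Patients with RECIST-defined PD may continue CPI therapy at the discretion of the treating MD". The trigger for coming off study is then a 20% or greater "increase in sum of target lesions compared to the initial PD tumor measurements".
- **Section 6.4 item 2**: "Patients on CPI treatment who develop a RECIST-PD (PD1) can continue CPI treatment if there is clinical benefit". The trigger there is: "If on subsequent imaging they continue to have RECIST-PD (PD2), they will be removed from trial".
- **Section 3.1, footnote 2** to the schema: CPI should stop at a subsequent progression. No reference scan or threshold is given.

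A separate note under the same schema reads: "Of note all imaging is compared to scans done prior to intermittent therapy initiation". Section 12.0 adopts RECIST 1.1 but does not define PD1, PD2 or progression after progression.

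**The concern.** Section 3.3 measures the second progression from the first-PD scan and requires new growth. Section 6.4 requires only that the patient is still in PD, so a stable tumour, or one that has shrunk a little, is enough for removal. Two sites reading different sections would make opposite decisions on the same scan.

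Removal also affects the data. Section 6.5 limits follow-up to at least 30 days after the last dose or until new anti-cancer treatment, whichever is earlier. Note 14 to the Section 11.0 calendar makes the removal visit the end-of-treatment visit. The rule in use therefore sets how long these patients are observed. It also decides whether they remain on trial long enough for a later tumour reduction to qualify them for the intermittent phase.

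**Working it through.** The plan gives no figure to reproduce. The check sets the two rules side by side and works out which scans they classify differently.

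**1. Do the rules cover the same patients?** Section 3.3 covers patients outside the intermittent phase who stay on CPI after RECIST-PD at the physician's discretion. Section 6.4 item 2 covers patients who reach PD on CPI and stay on it for clinical benefit. A patient outside the intermittent phase who continues CPI after a first PD falls under both.

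**2. Inputs**

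- PD threshold: an increase of at least 20%. The synopsis (Interventions) equates this with PD: "tumor burden (RECIST 1.1 PD) will re-initiate CPI". Section 3.3 uses the same percentage.
- *R*: the target-lesion sum against which the first PD was called. The documents give no sizes, so *R* = 100 is an assumption, held fixed at the next scan.
- First-PD sum: PD1 = *R*(1 + *g*), with *g* ≥ 0.20.
- *S*: the sum at the next scan.

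**3. Thresholds for leaving**

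- Section 6.4 item 2 (still in PD): *S* ≥ 1.20*R*.
- Section 3.3 (new growth over first PD): *S* ≥ 1.20 × PD1 = 1.20*R*(1 + *g*).
- Width of the disagreement: 1.20*R*(1 + *g*) − 1.20*R* = 1.20*Rg*.

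| First PD (*R* = 100) | 6.4 threshold | 3.3 threshold | Removed under 6.4, not triggered under 3.3 |
|---|---|---|---|
| 120 (+20%) | 120 | 1.20 × 120 = 144 | 120 to below 144 |
| 125 (+25%) | 120 | 1.20 × 125 = 150 | 120 to below 150 |
| 130 (+30%) | 120 | 1.20 × 130 = 156 | 120 to below 156 |
| 150 (+50%) | 120 | 1.20 × 150 = 180 | 120 to below 180 |

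**4. Two particular scans**

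- *No change after first PD* (*S* = PD1). Since 1.20*R* ≤ *R*(1 + *g*) < 1.20*R*(1 + *g*), this scan always falls in the band.
- *Some shrinkage*, from 130 to 121: (121 − 130)/130 = −6.9%. Because 121 ≥ 120, Section 6.4 removes the patient. Because 121 < 156, Section 3.3 does not.

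**5. Direction.** With *R* fixed and PD judged on target lesions, the 3.3 threshold is always the higher one. Every scan that triggers 3.3 also triggers 6.4, and the disagreement is always earlier removal under 6.4. Imaging for these patients is every 12 weeks, so the difference is at least one imaging interval for a patient who would otherwise have stayed on.

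**6. What does not depend on the choice.** The 36-week primary endpoint (Section 14.3), the 24-week stopping boundary (Section 14.2) and the target of 20 (Section 14.1) all concern patients who have suspended CPI. None of them uses the second-progression rule.

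**The case against.** **PD2 may be shorthand for the second progression that Section 3.3 defines.** Numbering it after PD1 suggests a new event, and footnote 2 of Section 3.1 fits that reading. But the operative words in Section 6.4 describe PD that persists, and the item neither defines PD2 nor refers to Section 3.3. The harmonised reading is possible, but the text does not establish it.

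**Section 3.3 does not oblige anyone to stay on CPI.** This is correct. Continuation is at the physician's discretion there and depends on clinical benefit in Section 6.4. The conflict is only about whether removal is triggered, and a reader should not infer that Section 3.3 keeps patients on treatment.

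**The disagreement may be short-lived.** Footnote 3 of Section 3.1 removes patients without more than a 10% reduction after two consecutive scans, and Section 6.4 item 6 does much the same for stable disease over 24 weeks. If these apply after PD, a patient who stays in the band leaves a scan or two later anyway. The documents do not say whether they apply, so this may limit the consequence but does not remove the contradiction.

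**A reader might infer a third competing reference from the schema note on imaging comparison.** The documents do not support this. The schema is not available in the text reviewed, so what the note attaches to is unknown. It refers to scans before intermittent therapy, and a patient who never entered that phase has no clearly distinct scan of that kind. The demonstrable conflict is between Sections 3.3 and 6.4.

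**A reader might also infer that slow responders to re-started CPI are removed too soon, biasing the re-initiation objective downwards.** The text does not establish this. The 3.3 rule sits in the paragraph on patients outside the intermittent phase. PD1 in Section 6.4 is progression that develops on CPI, whereas the progression that prompts a re-start develops off it. An effect is possible only if one of the rules is meant to extend to re-started patients, or if such a patient is later called PD1 while on CPI. The documents are silent on the first and do not exclude the second.

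**Conclusion.** The concern holds as a contradiction between two stated removal rules for patients continued on CPI after a first PD. With an assumed reference sum of 100, the same scan leads to opposite decisions over 120 to below 144 when first PD is at 120, and over 120 to below 180 when it is at 150.

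These figures assume that PD is judged on target lesions and that the reference sum is unchanged between the two scans. They do not cover progression by new lesions, which the Section 3.3 wording does not address. The documents give no basis for estimating how many patients would fall in the band.

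What is affected is when these patients leave the trial, how long they are followed, and whether they could later qualify for the intermittent phase. The primary endpoint, the stopping boundary and the sample size stand as they are.

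**What to change.** Reconcile Section 3.1 (footnote 2), Section 3.3 and Section 6.4 item 2 to one definition of second progression, with one reference scan and one threshold, and use the same term in all three. State whether that definition applies to patients who re-started CPI after progressing off therapy. Which rule applies is for the sponsor to decide.

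The cost is protocol wording only. No sample-size or boundary calculation needs to be redone.

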14.0 STATISTICAL CONSIDERATIONS

14.1 Sample Size Justification

In this phase II study, we will enroll at least 50 patients with advanced urothelial carcinoma who are refractory to first line therapy or who are cisplatin ineligible. Patients will be treated with CPI therapy for at least 20 weeks as per standard of care (SOC), at which time those with a tumor burden reduction of 10% or greater will suspend CPI therapy. If the number of patients with tumor burden reduction of $\geq 10\%$ after 20 weeks is less than 20 patients, we will continue enrollment up to a maximum of 75 patients until the target sample size of 20 complete or partial responders has been reached. If we are not able to enroll 20 patients to the intermittent arm, after enrolling 75 patients, then we will deem the trial not feasible.

14.2 Safety considerations:

The primary safety endpoint is progression at 24 weeks post CPI suspension. Based on Keynote 045, we expect approximately 40% of patients in this group to progress within one year,⁴⁵ we would consider a progression rate of 60% or more within the first 24 weeks of CPI suspension to be unacceptable. A higher than expected rate of rapid progression would indicate CPI suspension is not safe in this patient population. Accordingly, we have incorporated continuous safety monitoring stopping rules into our design to ensure patient safety (Table 1). Specifically, we will stop

Table 1: Bayesian safety monitoring stopping rules. E.g. if we observed 4 or more PD by week 24 out of the first 6 patients, the trial will stop early.

Total number of patients	Number of patients with PD at 24 weeks
6	4-6
7 – 8	5-8
9 – 10	6-10
11 – 12	7-12
13 – 14	8-14
15 – 17	9-17
18-19	10-19

the trial early and declare CPI suspension unsafe if there is strong evidence that CPI suspension results in higher than expected rates of progression at 24 weeks. We will use Bayesian safety monitoring and stop the trial early if $\text{Prob}(\text{PD}_{24 \text{ wk}} > 0.4 \mid \text{data}) > 0.85$. We use a beta (0.4, 0.6) prior for the true rate of progression at 24 weeks, which corresponds to a prior expected progression rate of 0.4. Table 1 shows the corresponding stopping boundaries. If a patient progressed or died of disease, or lost to follow-up before 12 weeks, then the patient will be considered failure. Table 2 summarizes the operating characteristics.

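### Section 3.3 tells patients already back on CPI to restart it when they respond again; the rule should almost certainly let them suspend it again

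*Combined protocol and SAP*

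**What the plan says.** Section 3.3 describes the cycle in three steps.

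- Patients who reach a tumor burden reduction of at least 10% enter the intermittent phase and "will not receive CPI therapy".
- If they progress while off drug: "Patients who have RECIST defined PD on the intermittent phase should reinitiate CPI therapy".
- The following sentence covers those who then have a further reduction of at least 10%. It says they "can then restart CPI therapy as per protocol", and it ends by pointing to the schema in Section 3.1.

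Three other places state what a 10% reduction triggers. The Synopsis (Interventions row) says, of the point after at least 20 weeks of CPI: "at which time those with a tumor burden reduction of 10% or greater will suspend CPI therapy". Section 3.1 says that patients with an initial reduction of this size stop, in the words "reduction will discontinue the CPI until they experience a", followed by a progression of 20% or more as the trigger for restarting. Section 14.1 repeats the Synopsis rule: "those with a tumor burden reduction of 10% or greater will suspend CPI therapy".

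**The concern.** The third step in Section 3.3 gives an instruction that its patients cannot carry out, because the second step has already put them back on CPI. It also points the wrong way: a response becomes the occasion for giving drug, whereas the rest of the plan makes it the occasion for withholding drug.

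This is an operative treatment rule, not background text. It decides whether a patient who responds, progresses off drug, resumes and responds again may have a second treatment holiday. Repeated on-and-off treatment is the strategy the trial is named for. A site that follows the words will continue CPI, while a site that follows the evident purpose will suspend it. With 20 patients planned for the intermittent arm, and a secondary objective on response to re-initiation (Section 2.2), inconsistent handling after re-initiation would make that part of the experience harder to describe.

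**Working it through.** No figure in the plan is at issue, so the check is a comparison of texts.

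**Step 1: trace one patient through Section 3.3.**

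1. Reduction of 10% or more on CPI: CPI stops, so the patient is off drug.
2. RECIST progression off drug: CPI is re-initiated, so the patient is on drug.
3. Further reduction of 10% or more: the text says to restart CPI, but the patient is already on drug.

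The instruction at step 3 leaves treatment unchanged.

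**Step 2: try the sentence on patients still off drug.** This does not rescue it. Shrinkage off therapy would become a reason to resume CPI, whereas the Synopsis says that patients who continue to respond remain off therapy.

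**Step 3: compare the direction of the rule across the document.**

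| Place | Trigger | Action |
|---|---|---|
| Synopsis, Interventions | reduction of 10% or more | suspend CPI |
| Synopsis, Interventions | increase of 20% or more | re-initiate CPI |
| Section 3.1 | initial reduction of 10% or more | discontinue CPI |
| Section 3.1 | progression of 20% or more | restart CPI |
| Section 3.3, criteria for the intermittent phase | reduction of 10% or more | no CPI |
| Section 3.3, progression in that phase | RECIST PD | re-initiate CPI |
| Section 14.1 | reduction of 10% or more | suspend CPI |
| **Section 3.3, sentence at issue** | **subsequent reduction of 10% or more** | **restart CPI** |

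The last row is the only readable statement that pairs shrinkage with giving drug.

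**Step 4: look for another rule that settles the matter.** Section 6.4 item 6 covers the opposite branch: a patient who on consecutive imaging "has SD while on therapy and does not achieve > 10% tumor burden reduction will be removed from the trial". Footnote 3 of Section 3.1 does the same. Neither says what happens to a patient who does reach the reduction a second time.

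**Step 5: see which analyses the sentence reaches.** It applies only after a patient has entered the intermittent phase, progressed, resumed CPI and responded again.

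- The primary endpoint (Sections 2.1 and 14.3) concerns the 36 weeks after suspension. A patient who has resumed CPI because of progression within that time has already failed it.
- The stopping rule (Section 14.2) counts progression by 24 weeks after suspension.
- The sample size (Section 14.1) counts entries to the intermittent arm.

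None of these depends on what is done at a second response.

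**The case against.** The strongest reply is that this is one missing word. The trial is titled as a study of intermittent therapy, and the sentence refers to the protocol and to the schema. Its natural meaning is that patients restart *intermittent* CPI. The schema may show that path clearly to sites, and its absence from the copy reviewed is no fault of the plan. Much of this stands: a drafting slip is the likeliest explanation, and the correction should be confirmed against the schema. It does not remove the point. The missing word reverses the instruction from giving drug to withholding it, and if the schema is right, the text contradicts it.

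A second reply is that the Synopsis, Section 3.1 and Section 14.1 describe the first reduction, so they do not strictly govern a second. That is fair. They show the direction of the strategy, not a rule for re-responders. The earlier line in Section 3.3 is more general and could be read to cover re-responders. A reader might infer that the plan has no rule for them at all, but that line and the unseen schema mean the documents do not support going so far. If the earlier line does cover them, the two sentences of Section 3.3 conflict.

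A third reply is that the wording is permissive, and that continuing CPI until progression or toxicity is usual practice, as the Synopsis background notes. That limits the harm to an individual patient. It does not make the sentence a usable rule for an intermittent strategy.

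A reader might also infer that the reference scan for the second 10% is left open, from the Section 3.1 note that "all imaging is compared to scans done prior to intermittent therapy initiation". That note is tied by an asterisk to the missing schema, so the imaging it governs cannot be established here. It is not part of this point.

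**Conclusion.** The sentence is wrong as written. Taken literally, it leaves re-responders on CPI when the strategy under study would allow a second hold. The error is minor, and its effect is confined to treatment after re-initiation and to later treatment-free intervals. A reader might infer that an error in the on/off rule undermines the main result. The documents do not support that, since the 36-week endpoint, the 24-week stopping rule and the sample size are all settled without this sentence.

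The number of patients affected cannot be stated, because the documents give no expected re-response rate. Confidence is high that the wording is faulty. That re-suspension was intended is an inference from the rest of the plan, subject to the Section 3.1 schema.

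**What to change.** Check the intended path in the Section 3.1 schema. If it shows a return to the off-treatment phase, replace the sentence in Section 3.3 with wording such as: *Patients whose tumor burden falls by ≥10% after re-initiation may suspend CPI again and re-enter the intermittent phase.* If the schema shows that CPI should continue, say that instead and remove the word for restarting.

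The cost is one sentence in a protocol amendment. The sample size, stopping boundaries and analysis stay as they are.

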4.0 SUBJECT SELECTION

Each of the criteria in the sections that follow must be met in order for a subject to be considered eligible for this study. Use the eligibility criteria to confirm a subject's eligibility.

4.1 Inclusion Criteria

Patients must meet all the following criteria to be eligible for study enrollment.

- Men and women ≥ 18 years of age.

- Histological confirmation of urothelial carcinoma (any histology)
- Advanced or metastatic urothelial carcinoma.
- Has received at least 20 weeks on CPI therapy per standard of care (SOC) for advanced urothelial carcinoma
- Karnofsky Performance Score (KPS) $\geq 70\%$ (for more information on KPS, please see: http://www.npcrc.org/files/news/karnofsky_performance_scale.pdf)
- Willing and able to provide informed consent.
- Laboratory criteria for study entry must meet the following criteria:
 - Serum creatinine $\leq 2 \times$ ULN OR CrCl $\geq 30 \text{ mL/min}$ (measured or calculated using the Cockcroft-Gault formula).
 - Hb $\geq 8.0 \text{ g/dL}$
 - AST and ALT $\leq 3.0 \times$ ULN
 - Bilirubin $\leq 1.5 \times$ ULN (except subjects with Gilbert Syndrome, who can have total bilirubin $< 3.0 \text{ mg/dL}$)

